OFFICIAL TITLE: Oral Health Educational Methods in Adolescence

NCT number: **03216746**

Date:17/07/2018

Study Protocol and Statistical Analysis Plan

Study population and sample size

The investigation followed the parameters of the Declaration of Helsinki and was approved by the Human Ethics Committee of the Federal University of Paraná (case number 51712315.4.0000.0102). The description of this clinical trial followed the recommendations made by CONSORT and the extension to cluster randomized trials¹⁹. The study was registered in the clinicaltrials.gov database under number NCT03216746.

Clinical trial randomized by clustering involving four arms in a 1: 1: 1: 1 ratio to the four intervention groups. The randomized allocation was performed using the classes as sample units. The courses were ordered alphabetically by name and allocation was generated by the software *Stata* version 12.0. A total of 28 classes were selected and randomly allocated to an interventional group by a blinded investigator, which did not participate in the study. The analysis was done in the individual unit. Adolescents of both sexes, aged 14 to 19 years, enrolled in a technical high school in the city of Curitiba, Paraná, Brazil were evaluated. Written informed consent was obtained prior to randomization from the participant or from the legal guardian when the age of the participant was less than 18 years.

Exclusion criteria were: adolescents with some physical or mental condition that made interventions impossible and those using fixed orthodontic devices at the time of clinical examination. Cluster unit areas of technical education related to the

health area, including dental technician, were excluded. The duration of the study was from July to December 2016.

The comparison between two independent groups was used for the sample calculation considering the unequal variances. For this calculation, the outcome was considered the "knowledge score" (KS). In a pilot study, it was found that the standard deviation of the KS from the "oral guidance" group was 2.56, while in the "video" group it was 1.96. In the same study, the difference detected between the groups was 0.53 points in the knowledge score. Therefore, considering a 5% significance level and 80% statistical power, a sample value of 108 individuals was found for each group, totaling 216 participants. Estimating a loss of 35% for each group, the final sample totaled 317 individuals.

Pilot study

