A pilot study was carried out with the objective of testing the suitability and methodological applicability of the instruments used. In addition, this step allowed us to verify the application dynamics of the instruments and the average time spent with each participant. Fifteen adolescents aged 14 to 19 years, with the same socioeconomic characteristics as the study population, were selected who did not participate in the main study. The methodological design was adequate; however, some terms of the questionnaire were modified to allow greater understanding on the part of the adolescents.

Interventions

Interventions were performed at the individual level within each cluster. The study included four phases (Figure 1), and the educational interventions or their different associations were evaluated through the knowledge score (KS) and oral

clinical indexes. In Phase I/baseline, the participants answered a questionnaire (pre-test) and were evaluated clinically. In phase II, the 28 classes were randomly allocated into two groups: 14 classes received oral guidance (OG) and 14 classes received video guidance (VG). Both methods (oral guidance and guidance by video) had the same thematic content. In the next phase (III), the groups were again divided into four groups (7 groups in each group), and for two of them, a smartphone App was developed so that reinforcement messages were sent during a period of 30 days. Shortly after this period (phase IV), the participants answered the questionnaire again (follow-up test) and were reassessed clinically.

Oral guidance with standardized content was performed by one of the researchers (GM) previously trained, and included aspects on general, oral health and, especially, on periodontal diseases. This guidance was carried out in the classroom, in a group, with approximately 20 adolescents, providing an environment of discussions on the subjects addressed. The duration was approximately 15 minutes. The elaboration of the video had the participation of three actors, two acting as adolescents and the third as a dental surgeon. The video had a total duration of 14 minutes and was applied in the classroom itself, in a group, with approximately 20 adolescents, without, however, allowing a later discussion of the subject.

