The "Oral Health" App was specially developed for this research and developed for the Android system version 4.4 (*Kitkat*) API level 19 with JAVA language (JDK 1.8.0) in the environment Android Studio 2.1.2, having 27.90 megabytes. The App has been made available for free on Google Play for 12,199 cellphone models. This tool was aimed at transmitting knowledge in oral health in a didactic, simple and relaxed way to its target audience over a period of 30 days. To this end, 60 messages were developed, based on the contents previously exposed in the educational activities, of which they were sent twice a day to each participant: the first with information in written form and the second in the form of videos, which had an average

duration of one minute, developed especially for this research and aiming to reinforce the content of the first tip.

The participant received messages developed through the Android notification bar. The standard tone and vibration of the phone were activated when receiving the messages. For the execution of these functionalities some permissions of the cellphone were necessary: permission to access the internet, to vibrate the cell phone, to keep the screen on while running the video and permission for the App start when the phone was turned on. The App performed its functions even when the cellphone was offline, requiring access to the Internet only at the time of downloading the App. The App source code can be obtained through the address in GitHub (<https://github.com/[name]/saudebucal>) and can be accessed and used by any user.

Questionnaires

Primary outcome was the knowledge score (KS) regarding etiology, treatment and forms of prevention of periodontal diseases. Data was obtained from a self-administered questionnaire, tested in a pilot study, using five statements: 1: If I have good oral hygiene I have less possibility of having gingival bleeding; 2: Whoever brushes their teeth very well does not need to floss; 3: It is not possible to remove the calculus or tartar with dental brushing; 4: Mouthwashes with mouth rinses may render flossing needless; and 5: A person may lose his teeth because he has problems in the periodontium. The answers were arranged in a three-point Likert scale, being *I agree*, *disagree* and *neither disagree nor disagree*. Correct answers were scored 1 (one), and incorrect and "do not know" score 0 (zero). Scores ranged from five (higher knowledge) to zero (less knowledge).

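### The stated sample size of 108 per group and its 80% power do not follow from the stated inputs, which give 291 per group two-sided (229 one-sided)

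*Combined protocol and SAP*

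**What the plan says.** All of this is in the combined protocol and SAP.

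- Study population and sample size, method: "The comparison between two independent groups was used for the sample calculation considering the unequal variances".
- Same section, inputs: the pilot "standard deviation of the KS from the 'oral guidance' group was 2.56, while in the 'video' group it was 1.96". The planning difference is 0.53 KS points, also taken from the pilot. The significance level is 5% and the power 80%; whether the test is one- or two-sided is not said.
- Same section, result: "a sample value of 108 individuals was found for each group", so 216 in all before the allowance for loss.
- Questionnaires: the knowledge score (KS) is the primary outcome. It sums five items, each scored 1 if correct and 0 otherwise: "Scores ranged from five (higher knowledge) to zero (less knowledge".
- Pilot study: after the pilot, "some terms of the questionnaire were modified to allow greater understanding on the part of the adolescents".
- Randomisation was by class, with 28 classes. The sample-size paragraph makes no allowance for this.

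**The concern.** The paragraph names its method and gives every input except sidedness, so a reader can repeat the calculation, and it does not return 108. The gap is more than twofold, well beyond rounding or a choice between normal and t approximations.

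There is also a secondary sign of trouble. One of the two SDs is larger than the population SD of a 0-5 score can be, which suggests that the pilot figures are mislabelled or belong to a different scale.

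The KS is the primary outcome. A non-significant comparison of oral guidance with video could be read as coming from a trial with 80% power for 0.53 points, when the plan's own figures do not support that description.

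**Working it through.** **Inputs** (Study population and sample size): SD1 = 2.56, SD2 = 1.96, difference d = 0.53, 5% significance, 80% power, equal groups. Normal quantiles: 1.960 (two-sided 5%), 1.645 (one-sided 5%), 0.8416 (80% power).

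**Formulas**, with V the sum of the two group variances:

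- n per group = (z_alpha + z_beta)² × V / d²
- power at 108 = Phi(d / sqrt(V/108) − z_alpha)
- difference detectable with 80% power at 108 = (z_alpha + z_beta) × sqrt(V/108)

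**Step 1. Try to reproduce 108 by the stated method.** V = 2.56² + 1.96² = 6.5536 + 3.8416 = 10.395.

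- Two-sided: 2.8016² × 10.395 / 0.2809 = 290.46, so 291 per group. The Welch t calculation gives 292.
- One-sided: 2.4865² × 10.395 / 0.2809 = 228.80, so 229 per group.

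Neither is 108.

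**Step 2. What 108 gives on the stated inputs.** sqrt(10.395/108) = 0.3102 and 0.53/0.3102 = 1.708.

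- Power two-sided: Phi(1.708 − 1.960) = 40%.
- Power one-sided: Phi(1.708 − 1.645) = 53%.
- Detectable difference, two-sided: 2.8016 × 0.3102 = 0.87.

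**Step 3. Check the SD against the score.** On a 0-5 score the largest population SD is 5/2 = 2.5, reached only with half the people at 0 and half at 5. As a sample SD (n−1 divisor) the ceiling at n = 108 is 2.5 × sqrt(108/107) = 2.512. In a very small sample the ceiling is higher: in a group of 7 or 8 it is 2.67, and the scores 0,0,0,1,5,5,5 have an SD of 2.56. So 2.56 can occur as a small pilot estimate, but only with nearly everyone at an extreme.

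**Step 4. Other readings of the same figures.**

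| Reading | V | n two-sided | n one-sided | Power at 108, two-sided | Power at 108, one-sided | Detectable difference, two-sided |
|---|---|---|---|---|---|---|
| As stated | 10.395 | 291 | 229 | 40% | 53% | 0.87 |
| 2.56 lowered to 2.5 | 10.092 | 282 | 223 | 41% | 54% | 0.86 |
| 2.56 and 1.96 are variances | 4.52 | 127 | 100 | 74% | 83% | 0.57 |

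No row returns 108. The bound breach alone moves n by 291 − 282 = 9 per group and power by about 1 point, and it errs toward a larger trial.

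**Step 5. Which SD would support the claim.** With a common SD s, V = 2s². Setting n = 108 two-sided gives s = 0.53 × sqrt(54) / 2.8016 = 1.39, before clustering.

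**Step 6. Allowance for classes.** With 216 analysed in 28 classes, the mean is 7.71 per class. The documents give no intraclass correlation (ICC). Assuming 0.01 to 0.10, the design effect 1 + 6.71 × ICC is 1.07 to 1.67. The limit of 1.39 in Step 5 then falls to 1.39/sqrt(1.07) = 1.34 or 1.39/sqrt(1.67) = 1.08. On the stated inputs, 0.87 becomes 0.90 to 1.12.

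**The case against.** The strongest reply is that the 40% rests on an SD that this point itself calls doubtful, so it cannot show that the trial was underpowered. That is right. A reader might infer that the trial really had 40% power, or that no correction of the SDs could bring it back to 80%. The documents support neither. Any common SD up to about 1.39 gives 80% two-sided power at 108 before clustering. As an illustration only, five independent 0/1 items cannot have an SD above sqrt(5 × 0.25) = 1.118, which needs 70 per group; positively correlated items could exceed that. The documents do not settle the true SD.

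A second reply is that 2.56 and 1.96 are exact squares (1.6² and 1.4²), so they may be variances. With a one-sided test, power at 108 is then 83%, above the claim. This needs two departures from the text: relabelling what it calls a standard deviation, and a one-sided test that it never mentions. It also gives 100, not 108.

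Two calculations do land near 108. The variance 1.96² used alone gives 7.849 × 3.8416 / 0.2809 = 107.3, rounded up to 108. A common variance of 1.96 gives 110. A reader might infer that one group's variance was dropped. Nothing in the documents shows this, and both calculations contradict the stated unequal-variance method for two groups.

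A reader might also try to prove the three pilot figures jointly impossible from the size of the pilot ("Fifteen adolescents aged 14 to 19 years, with the same socioeconomic characteristics as the study population, were selected"). The Pilot study section mentions no oral and video groups and no split, so that argument rests on a guess and is not used here.

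What stands is that none of these replies makes the paragraph correct as written.

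**Conclusion.** The sample-size statement is wrong as written and should be corrected. By its own method and inputs the requirement is 291 per group two-sided or 229 one-sided, against 108 stated. On those inputs 108 per group has 40% or 53% power, against 80% stated, with 0.87 points detectable two-sided instead of 0.53. These results assume equal groups and a normal approximation (Welch t differs by one person per group) and make no allowance for classes. They are consistency checks on the stated inputs.

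The SD of 2.56 is secondary. It exceeds the population maximum of 2.5 and so casts doubt on the label or scale of the pilot figures, but has little numerical effect by itself. Confidence in the failure to reproduce 108 is high; its cause is not shown in the documents.

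**What to change.** 1. State which score the pilot figures refer to and its range, the pilot group sizes, and whether 2.56 and 1.96 are SDs or variances.
2. State the sidedness and the formula, show whether both group variances entered it, and correct the calculation.
3. Withdraw 80% power as a result derived from the stated inputs.
4. Report instead the detectable difference, or the power for 0.53, at the size analysed. Use an SD that is feasible for the 0-5 score, for example the pooled Phase I KS SD, labelled as a proxy for the follow-up SD. Include a design effect for the 28 classes, with the ICC stated as an assumption and shown over a range.

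Whether 80% power is then reached depends on that SD and the ICC, and should not be prejudged.

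The cost is one rewritten paragraph and one descriptive statistic from data already collected. The study ran from July to December 2016, so the gain is accurate reporting and no design change is possible. The downside is that the reported power may become less favourable.

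### The difference and SDs behind the sample size are observed pilot values, apparently from 15 adolescents, too imprecise to support the stated 80% power

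*Combined protocol and SAP*

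**What the plan says.** Under Study population and sample size, the inputs are introduced with "In a pilot study, it was found that the standard deviation of the KS" and given as 2.56 for oral guidance and 1.96 for video. The target follows from the same source: "the difference detected between the groups was 0.53 points in the knowledge score". From these, with 5% significance and 80% power, the section derives 108 per group (216 in total), and 317 after allowing for 35% loss. The stated method compares two independent groups with unequal variances.

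The Pilot study section describes one pilot only. It enrolled "Fifteen adolescents aged 14 to 19 years" and was run "with the objective of testing the suitability and methodological applicability of the instruments used", and to check how the instruments were applied and how long each participant took. Estimating an effect is not among its aims. Afterwards "some terms of the questionnaire were modified to allow greater understanding on the part of the adolescents".

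The Questionnaires section defines the KS as the number of correct answers to five statements, so it takes whole values from 0 to 5. No section says why a 0.53-point difference matters, and none allows for uncertainty in the pilot values.

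**The concern.** A power statement is only as good as the difference and SD it is computed for. Here both are sample estimates from what appears to be a very small instrument-testing exercise, used as if they were known. The target is what the pilot happened to show, not a difference the investigators set out to detect.

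At stake is what a reader may conclude from the 80% figure. It suggests that the oral-versus-video comparison was well powered for a meaningful gap in knowledge. If the inputs are unreliable, that reassurance is not available, and a non-significant comparison could be over-read as evidence that the methods are equivalent.

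**Working it through.** **Inputs from the documents.** Difference d = 0.53; SDs 2.56 and 1.96; significance 5%; power 80%; 108 per group; pilot total 15; KS range 0 to 5.

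**Assumptions.** Two-sided testing (sidedness is not stated); the pilot behind the inputs is the 15-adolescent pilot; a split of 8/7 or 7/8 (the split is not stated).

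**1. The plan's own figure.** For two independent means with unequal variances, n per group = (SD1² + SD2²)(z₀.₉₇₅ + z₀.₈₀)² / d².
- SD1² + SD2² = 6.5536 + 3.8416 = 10.3952.
- (1.960 + 0.842)² = 7.849.
- n = 10.3952 × 7.849 / 0.2809 = 290.5, so 291 per group. One-sided, it is 229.

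The stated 108 is not reproduced. Of the variants tried, only a one-sample or paired formula with the video SD alone comes to it: (1.96 × 2.80 / 0.53)² = 107.3. That is not the method the section names.

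**2. Power of 108 per group on the printed inputs.** SE = √(10.3952/108) = 0.310. Power = Φ(0.53/0.310 − 1.960) = Φ(−0.25) = 40% (53% one-sided). The difference detectable with 80% power is 2.80 × 0.310 = 0.87 points.

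**3. Precision of the pilot difference (Welch).** For an 8/7 split, SE = √(6.5536/8 + 3.8416/7) = √(0.8192 + 0.5488) = 1.17, with 12.8 df and t = 2.16. The 95% CI is 0.53 ± 2.53, that is −2.00 to 3.06; p = 0.66.

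| Oral / video | SE | 95% CI |
|---|---|---|
| 8 / 7 | 1.17 | −2.00 to 3.06 |
| 7 / 8 | 1.19 | −2.08 to 3.14 |
| 10 / 5 | 1.19 | −2.12 to 3.18 |
| 5 / 10 | 1.30 | −2.60 to 3.66 |

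The SE is more than twice the estimate whatever the split. The plan does not say which group scored higher, so the sign of the difference is arbitrary.

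**4. Is an SD of 2.56 possible?** On a 0-5 score the population SD is largest when half score 0 and half score 5, which gives 2.5. A sample SD can go slightly higher: with 7 or 8 scores the maximum is 2.67. So 2.56 is attainable in a tiny sample only if nearly all scores are 0 or 5. As a planning value for the population it is impossible.

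**5. Does 0.53 fit this pilot?** With all 15 adolescents in two separate groups and whole-number scores, no split gives a difference in means that rounds to 0.53; a 7/8 split comes closest, at 30/56 = 0.536. Either the figure was truncated, or not all 15 contributed, or the scoring or grouping differed from what is described. If there had instead been 15 in each group, SE = √(10.3952/15) = 0.83 and the 95% CI would be about −1.2 to 2.2, which still covers zero.

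**The case against.** The strongest reply is that the link between the two sections is inferred. The sample size section says only that there was a pilot with oral and video groups. The Pilot study section mentions no intervention groups, no comparison of scores and no split. That stands, and step 5 of the working adds to it. But no other pilot is described, and even 15 per group would leave the difference indistinguishable from zero.

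The Welch interval also uses SDs that are themselves suspect. That is fair: it shows what the printed figures imply and does not estimate the truth. For the same reason, a normal-theory interval for the SD of 2.56 (1.7 to 5.2 with 8 adolescents) should not be relied on, because most of it lies above the possible maximum of 2.5.

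Several stronger readings are tempting, and the documents do not support them:
- A reader might infer that 0.53 points is not worth detecting. The documents show only that its importance was never argued; about half of one statement in five could matter educationally.
- A reader might infer that a null result cannot be interpreted. It can, from the estimate and its confidence interval, whatever the planning target was.
- A reader might infer that the pilot used a different version of the primary outcome. The text says some terms changed, not that the five KS statements or their scoring did.
- A reader might be struck that n varies about elevenfold between targets of 0.30 and 1.0 points. That ratio is (1.0/0.30)² = 11.1 in any comparison of two means and says nothing particular about this trial.

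Finally, the study ran from July to December 2016 and the document is dated July 2018, so any target set now is retrospective. That limits the remedy to correcting the power statement.

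**Conclusion.** The concern holds in a limited form. The 80% power statement rests on three observed values from what appears to be a 15-adolescent instrument-testing pilot. One of them is above the possible population maximum for the score, and the difference has a 95% CI of about −2.0 to 3.1 under a near-equal split. The 0.53-point target is unjustified, which is not the same as unimportant.

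Taken at face value, the printed inputs give 108 per group about 40% power, not 80%. If the true SD is below the printed values, as the 0-5 range suggests for 2.56, power would be higher than that; by how much cannot be said from the documents. These figures assume two-sided testing and independent participants. Allowing for clustering by class would lower the power.

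**What to change.** In the sample size section, make these changes:

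- Stop presenting the pilot difference as the target. If a smallest worthwhile KS difference is given, justify it in terms of statements answered correctly and label it as chosen afterwards.
- Replace the pilot SDs with the pooled KS SD from Phase I. Those data come from the main study's pre-test and, on the Interventions section's account, precede the Phase II allocation. State that the SD at follow-up may differ.
- Restate the power of the actual sample as a short table at 0.3, 0.5, 0.75 and 1.0 points. For orientation, 108 independent participants per group with the printed SDs give about 16%, 36%, 68% and 90%.
- Name the contrast: oral versus video, or pairs of the four arms. The present calculation covers two groups only; four equal arms of 317 would have about 79 each before losses.
- Include a design effect, 1 + (m − 1) × ICC, over a stated ICC range. The documents give no ICC. With assumed values of 0.01 to 0.05, m = 317/28 ≈ 11.3 gives 1.10 to 1.52, and about 20 per class (the group size given for the sessions) gives 1.19 to 1.95.

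The cost is one paragraph and one small table, from data already collected. No extra enrolment is needed. This is not an observed-power calculation, since no observed treatment effect enters it. The downside is that the stated power may be less favourable.

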Those responsible for adolescents also answered a questionnaire containing socioeconomic and demographic information according to criteria of the Brazilian Association of Research Companies²⁰.

Oral clinical examination

Clinical examination was performed by a single examiner calibrated ($K \geq 0.83$) and blinded as to the intervention used and which verified the presence of dental biofilm through the simplified oral hygiene index (OHI-S)²¹ and gingival bleeding (GBI)²². The tests were performed in two stages: Phase I and 20 weeks after in Phase V (Figure 1). The subjects were examined in a classroom where they were seated in chairs, and the evaluations were done individually, using gauze, artificial light and a millimeter probe.

Statistical analysis

Statistical analysis was performed on an individual level. Chi-square test was used to analyze the categorical variables. The numerical variables were submitted to the *Kolmogorov-Smirnov* test to verify the normality of the data, obtaining values of $P < 0.05$. Thus, non-parametric tests were used to verify the association between the means of KS, OHI-S and GBI among the different intervention groups. The OHI-S variable was dichotomized in: $OHI-S > 1$ (high dental biofilm index) and $OHI-S \leq 1$ (low dental biofilm index). *Kruskal Wallis* and *Mann-Whitney* tests were used for independent samples and *Wilcoxon's* test for paired samples. The level of significance adopted for all analyzes was 5%. The analyzes were performed using SPSS software version 20.0 (SPSS Inc., Chicago, IL, USA).

[figure not shown]

Figure 1. Flow chart demonstrating the different phases of the study.

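### The printed pilot values do not give 108 per group: the stated method needs 291 (two-sided) or 229 (one-sided), and power at 108 is about 40% or 53%, not 80%

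*Combined protocol and SAP*

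**What the plan says.** Under Study population and sample size, the method is given as follows: "The comparison between two independent groups was used for the sample calculation considering the unequal variances". The outcome is the knowledge score (KS), which the Questionnaires section names as primary.

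The inputs come from pilot work. "In a pilot study, it was found that the standard deviation of the KS from the" oral-guidance group was 2.56, and the video group's was 1.96. For the effect, "the difference detected between the groups was 0.53 points in the knowledge score". The result is then stated: "considering a 5% significance level and 80% statistical power, a sample value of 108 individuals was found for each group, totaling 216 participants". A loss allowance follows: "Estimating a loss of 35% for each group, the final sample totaled 317 individuals".

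Two other places bear on this. Questionnaires gives the range of the outcome: "Scores ranged from five (higher knowledge) to zero (less knowledge"). Statistical analysis says only "The level of significance adopted for all analyzes was 5"%, with no mention of one or two sides.

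**The concern.** Every input except the sidedness is printed in one paragraph, so the 108 can be checked directly, and it looks far too small. The squared standard deviations sum to more than 10, while the difference is only about half a point.

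The 80% power statement is the only justification given for the sample size on the primary outcome. A reader will take 0.53 points as a difference the study was likely to detect. If power was really about half of what is claimed, a null result for oral guidance against video could be misread as evidence that the two methods teach equally well.

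**Working it through.** **Inputs (Study population and sample size).** SD 2.56 (oral) and 1.96 (video); difference 0.53; 5% significance; 80% power; equal groups. Because the sidedness is not given, both cases are shown.

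**Formula.** n per group = (z_α + z_β)² × (SD₁² + SD₂²) / d²

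- Sum of variances: 2.56² + 1.96² = 6.5536 + 3.8416 = 10.3952
- d² = 0.53² = 0.2809
- (1.960 + 0.842)² = 7.849 two-sided; (1.645 + 0.842)² = 6.183 one-sided

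**Attempt to reproduce 108.**

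- Two-sided: 7.849 × 10.3952 / 0.2809 = 290.5, so 291 per group (292 with the Welch t version). 291/108 = 2.7.
- One-sided: 6.183 × 10.3952 / 0.2809 = 228.8, so 229 per group (230 with Welch t). 229/108 = 2.1.

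Neither gives 108. Rounding of the inputs does not explain it: with SDs of 2.555 and 1.955 and a difference of 0.535, the results are still 284 and 224.

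**What 108 per group delivers.** The standard error of the difference is √(10.3952/108) = 0.310, and 0.53/0.310 = 1.708.

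| | Two-sided | One-sided |
|---|---|---|
| Power | Φ(1.708 − 1.960) = 40.1% (Welch t 39.8%) | Φ(1.708 − 1.645) = 52.5% (Welch t 52.3%) |
| Difference detectable with 80% power | 2.802 × 0.310 = 0.87 | 2.486 × 0.310 = 0.77 |

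If all 317 were analysed as two groups of 158.5, power would be 54% two-sided or 66% one-sided.

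**Where 108 might come from (inference only).** Working backwards, two-sided, 108 × 0.2809 / 7.849 = 3.865. Taking off the video variance of 3.8416 leaves about 0.024, which is an oral SD of at most about 0.15. So 108 leaves almost no room for the oral group's variance. A one-sample formula with the video SD alone gives 7.849 × 3.8416 / 0.2809 = 107.3, which rounds up to 108. That is not the stated method.

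**Are the printed SDs plausible?** On a 0 to 5 score no population SD can exceed 2.5. A small sample can show 2.56: the maximum is 2.67 in a group of 7 or 8. Capping the oral SD at 2.5 gives 7.849 × (6.25 + 3.8416) / 0.2809 = 282 per group, and two-sided power at 108 of 41%.

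**If the values are variances (conjecture).** 2.56 = 1.6² and 1.96 = 1.4², so variances may have been printed as SDs. The sum is then 4.52.

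| | Two-sided | One-sided |
|---|---|---|
| n per group | 7.849 × 4.52 / 0.2809 = 126.3, so 127 | 6.183 × 4.52 / 0.2809 = 99.5, so 100 |
| Power at 108 | 74% | 83% |
| Detectable difference at 108 | 0.57 | 0.51 |
| Power if all 317 are analysed | 88% | 93% |

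Allowing for rounding of the inputs, n runs from about 124 to 129 two-sided and 97 to 102 one-sided. Neither range contains 108.

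**Loss allowance (minor).** 216 / 0.65 = 332.3, so 333, not 317. Conversely, 1 − 216/317 = 31.9%, not 35%.

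**The case against.** The strongest reply is that the inputs are themselves in doubt, so 40% should not be taken as the true power. The pilot described had fifteen adolescents. Enumerating whole-number scores from 0 to 5, an SD of 2.56 arises only in groups of 7 or 8, and no two-way split of fifteen gives a mean difference that rounds to 0.53. If that pilot and that score were the source, the printed inputs cannot all be right. Across the readings above, power at 108 runs from 40% to 83%, so at the favourable end nothing is overstated.

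This stands as a limit on the replacement figures: 291, 40% and 0.87 hold only if the printed SDs do. It does not rescue the paragraph. It adds a reason to go back to the pilot data, and the favourable end needs both an input that is not printed and a sidedness that is not stated. The one-sample formula also reaches 80% at 108, but it is not a comparison of two groups.

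A second reply is that the study ran from July to December 2016, so no design or analysis decision can change, and 108 does not enter the planned tests. That is true, and it is why only a text correction is asked for. The power claim still governs how a null result will be read.

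Third, 317 may be the number recruited rather than a target. The wording allows this, so the loss step is a minor point.

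**Conclusion.** The concern holds. From its own printed inputs and stated method, the plan needs 291 per group two-sided or 229 one-sided. At 108 per group, power is about 40% or 53%, which is 40 or 27 percentage points below the claim. No reading of the two values, as SDs or as variances, one-sided or two-sided, gives 108 with the two-group formula.

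That 108 does not follow is certain. The size of the shortfall depends on the printed SDs being correct; if they are variances, it shrinks to 127 against 108 two-sided and disappears one-sided.

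All figures are for two groups compared on means and are before any design effect. The trial has four arms, and 28 classes were randomised, so positive correlation within classes would lower power further. Power for the planned Mann-Whitney test would need the pilot score distributions, which are not given.

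**What to change.** 1. Go back to the pilot data and confirm 2.56, 1.96 and 0.53, including whether the first two are standard deviations or variances and whether the pilot score was the same five-item score. Print the sidedness and the formula actually used.
2. Then restate the required number and the power or detectable difference at 108 per group:
   - Printed SDs confirmed: 291, 40% and 0.87 two-sided, or 229, 53% and 0.77 one-sided.
   - Values confirmed as variances: 127, 74% and 0.57 two-sided, or 100, 83% and 0.51 one-sided.
   - Other values found: recompute with the same formula.

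   Present this as a correction of the planning calculation, not as power computed from the trial's results. Say that it covers the two-group comparison before any design effect for the 28 classes.
3. Minor: correct the step from 216 to 317 (333 at 35% loss; 317 allows 31.9%), or say that 317 is the number recruited.

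The cost is a check of the pilot records and a revised paragraph, with no added enrolment. The downside is a less favourable stated power, unless the values prove to be variances and the test one-sided.
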